10.5. Subgroup Analyses

Between subject subgroup analyses will include the following subgroups:

- Primary disease
- Type of hospital ward
- Body weight in quartiles
- Study site

Each subgroup analysis will be based on a one-way analysis of variance on the individual RMSDs which includes the subgroup as the factor. Each analysis will be done at a significance level of 0.05.

Within subject subgroup analyses will be performed to compare results under awake and asleep conditions. The RMSD will be calculated for each subject while awake and while asleep. Mean RMSDs will be compared by paired t tests at a significance level of 0.05.

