The RHEA Vital Sign Vigilance System was developed by Shenzhen Fiber Medical Technology Co. Ltd. It is designed for automatic, continuous and contact-less measurement of heart rate and respiratory rate of patients in a hospital or clinic setting. The system uses a sensor placed under the patient's mattress, and does not require a sensor to be fixed to the body. This provides a more comfortable solution for long-term continuous patient monitoring. Continuous monitoring of people's vital signs, in particular heart rate (HR) and respiratory rate (RR), may provide a mechanism to alert doctors or nurses of disease deterioration or an imminent severe clinical event. Monitoring people's vital signs outside an ICU often relies on nursing staff conducting checks at set intervals. The device can reduce the workload for nursing staff in non-ICU wards. The FDA-cleared EarlySense System 2.0 (K131379) developed by EarlySense Ltd. is also a contact-less system designed for continuous monitoring heart rate and respiratory rate of patients. It has been sold in over 20 U.S. hospitals since 2013. No recalls and adverse events have been reported. According to publicly available clinical results, the EarlySense System has shown an 86% reduction in Code Blue events, and a 45% reduction in Length of Stay (LoS) in the ICU for patients coming from the medical/surgical unit (1, 2). The EarlySense device applies the piezoelectric sensor while in comparison, the RHEA investigational device applies the optical fiber sensor. This difference leads to the RHEA device having a higher accuracy, capacity for greater patient weight range, longer sensor life and a lower cost. A Pilot Study on 25 healthy volunteers (20 adults and 5 children) showed that the RHEA device can obtain accuracy of overall mean root mean square difference (RMSD) of both HR and RR of 1.9 with the same testing procedure described in this current protocol (3). When comparing with the reference device- the EarlySense device on 9 adults, the RHEA device obtained results with no significant difference (pair t test is used to evaluate the results according to this protocol.)

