4.1. Inclusion Criteria

Subjects will be included if they meet the following inclusion criteria:

1. Male or female, 18 years old and above.
2. Provide written informed consent.
3. Weight ranging from 20 to 150 kg inclusive.
4. Are located in a non-ICU hospital setting.
5. Agree to not eat during the testing period.
6. Agree to keep still.

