10.3. Primary Analyses

For each subject, the RMSD will be calculated for both HR and RR. These individual values will be presented in both a listing and graphically as a cumulative distribution. The mean RMSD and its two-sided 95% confidence interval (mean RMSD \pm $t_{0.975} * \text{std err RMSD}$) will be presented. If the upper bound of the confidence interval is less than the hypothesized value, the corresponding null hypothesis will be rejected. For each rejected hypothesis, the study will have met its primary objective.

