10.6. Sample Size

In a pilot study of 20 adult healthy volunteers with 20 paired observations each, the standard deviation of their RMSDs vs. the reference method were found to be approximately 0.75 for both HR and RR (2). Based on this standard deviation, 73 adult subjects will provide 80% power to reject each primary hypothesis if the population mean RMSD for HR is 3.0 and the population mean for RR is 2.0. To account for a dropout rate as high as 5%, a total of 77 adult subjects will be enrolled.

SAS Version 9.4 PROC POWER was used for all sample size calculations.

11. Regulatory and Reporting Requirements

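### Body weight is analysed only as sample quartiles in an unordered ANOVA; a prespecified continuous-weight model with curvature should be added beside it

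*Combined protocol and SAP*

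**What the plan says.** Section 10.5 (Subgroup Analyses) lists four between-subject factors: primary disease, ward type, "Body weight in quartiles" and study site. The method is the same for all four: "Each subgroup analysis will be based on a one-way analysis of variance on the individual RMSDs which includes the subgroup as the factor". On the error rate it adds: "Each analysis will be done at a significance level of 0.05". Section 10.5 specifies no slope, trend contrast, plot against weight or fitted RMSD at a given weight.

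The eligibility rule in Section 4.1 is "Weight ranging from 20 to 150 kg inclusive", and Section 5.1 gives the intended use as adults up to 150 kg. Section 2.1 (Background and Rationale) credits the device, relative to EarlySense, with "capacity for greater patient weight range". Section 6.2 has weight recorded at baseline. Section 10.1 enrols consecutively, with no weight strata. Section 10.3 provides a listing and a cumulative distribution of the individual RMSDs, neither tied to weight.

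**The concern.** Disease, ward and site are categories by nature. Weight is the only listed between-subject factor that the plan makes categorical by choice. It is also the one most closely tied to how the device works, since the sensor lies under the mattress and reads small vibrations, and the intended use is bounded by weight.

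The quartile ANOVA spends three degrees of freedom, treats the four groups as unordered, uses cut points that depend on who happens to enrol, and discards variation within each group. With 73 subjects the top group holds about 18, over whatever range they span. If accuracy drifts with weight, or worsens gradually towards the heavy end, the plan's only weight analysis may miss a pattern that the same data would show in a continuous model.

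**Working it through.** **1. The plan's own figure.** Section 10.6 gives an SD of 0.75 and power "if the population mean RMSD for HR is 3.0 and the population mean for RR is 2.0", against null values of 3.25 and 2.25, so the difference is 0.25 for each variable. Section 10.3 bases the decision on "The mean RMSD and its two-sided 95% confidence interval". The noncentrality is (0.25 / 0.75) × √73 = 2.848 on 72 df, which gives 80.2% power (72 subjects give 79.7%). For dropout, 73 / 0.95 = 76.8, so 77. Both figures reproduce. The documents state no power for the weight analysis.

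**2. Straight-line relation.** n = 73, two-sided 5%; r is the correlation of RMSD with weight (assumed).

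- Slope test: F(1, 71), noncentrality n r² / (1 − r²).
- Quartile ANOVA: F(3, 69), noncentrality n c r² / (1 − c r²), where c is the share of weight variance lying between quartiles. For normal weight the quartile means lie at about ±0.32 and ±1.27 SD, so c ≈ (0.32² + 1.27²) / 2 ≈ 0.86.

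Example, r = 0.30: slope 73 × 0.09 / 0.91 = 7.22; ANOVA 73 × 0.0774 / 0.9226 = 6.12. The noncentrality falls only modestly. The rest of the loss comes from spending 3 df in place of 1.

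| r (assumed) | slope power | ANOVA power | relative loss |
|---|---|---|---|
| 0.20 | 40.5% | 23.0% | 43% |
| 0.25 | 58.6% | 35.2% | 40% |
| 0.30 | 75.5% | 50.2% | 34% |
| 0.35 | 88.3% | 66.1% | 25% |
| 0.40 | 95.7% | 80.4% | 16% |
| 0.50 | 99.8% | 96.7% | 3% |

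At r = 0.30 the loss is 28% if weight is uniform (c = 0.937) and 36% if it is lognormal with log-SD 0.25 (c = 0.832). At r = 0.315, where the slope test has 80% power, the ANOVA has 55.1% and would need 121 subjects to reach 80%.

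**3. Other shapes.** Simulated power at n = 73 with normal weight. Effects are assumed and expressed in residual SDs. The joint 2-df test of weight and weight squared is compared with the quartile ANOVA; both hold their 5% level.

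| Pattern | 2-df model | quartile ANOVA |
|---|---|---|
| Linear, r = 0.30 | 64% | 49% |
| Rise from the 75th percentile, 1.0 per SD of weight | 66% | 38% |
| Rise from +1 SD, 1.5 per SD of weight | 65% | 28% |
| Heaviest 10% raised by 1.2 | 52% | 27% |
| Symmetric smooth U, sized so that the ANOVA has 27% | 71% | 27% |
| Step of 0.8 at the top-quartile cut | 53–55% | 56–68% |
| Steps of 0.8 at both outer cuts | 40–43% | 63–81% |

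In the last two rows the lower ANOVA figures put the step at the population quartile, and the higher ones at the sample quartile that the ANOVA itself uses.

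**4. The upper limit.** The documents give no weight distribution, so two are assumed.

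- Mean 80, SD 20 kg: the top quartile starts at 80 + 0.6745 × 20 = 93.5 kg and averages 80 + 1.271 × 20 = 105.4 kg. About 0.5 of 73 subjects would exceed 130 kg.
- Mean 90, SD 25 kg: it starts at 106.9 kg and averages 121.8 kg. About 4 of 73 would exceed 130 kg.

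A top-quartile mean therefore describes weights well below 150 kg. A straight line carried to 150 kg has SE 0.75 × √(1/73 + ((150 − m)/s)² / 72), with m and s the mean and SD of weight: 0.32 for the first case and 0.23 for the second (0.48 for mean 70, SD 15). A quartile mean has SE 0.75 / √18.25 = 0.18. The fit at 150 kg would be mostly extrapolation.

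**The case against.** The best defence is that an unordered ANOVA assumes no shape. Step 3 bears this out: if error jumps at the quartile cuts, above all at both ends, the ANOVA beats the quadratic model, and it beats a bare slope as well (65% against 54% for a top-quartile step of 0.8 SD). An under-mattress sensor could do worse at both extremes of 20 to 150 kg. The squared term also costs power when the truth is a straight line (75% for the slope alone, about 64% for the joint test). All of this stands, and it is why the ANOVA should not be dropped.

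A reader might infer more than the documents support:

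- *That the plan simply loses a third of its power.* That figure needs a moderate linear relation. The documents give neither the size nor the shape of any relation, nor the weight distribution.
- *That quartiles cause the lack of information near 150 kg.* Section 10.1 enrols consecutively, so there may be few heavy subjects under any analysis, and regression cannot supply them. Nor is the plan wholly silent: weight is recorded and individual RMSDs are listed, though no planned analysis links them.
- *That regression could replace the ANOVA at no loss.* The two step patterns show otherwise.
- *That a non-significant result will be taken as proof that weight does not matter.* Section 10.5 does not say so. No success criterion depends on the subgroups, and the weight-range advantage is background, not a hypothesis.

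**Conclusion.** The point holds as a low-cost improvement. It is not an error in the plan. For a smooth relation between weight and RMSD, the quartile ANOVA is the weaker tool: 25% to 40% less power than a slope test at assumed correlations of 0.35 down to 0.25. For a gradual rise among the heaviest subjects it has 28% to 38% power, where a quadratic model has about 65%. For jumps at the quartile cuts the ordering reverses. No single test is best across these patterns, so the case is for adding a continuous model. These sizes rest on 73 analysed subjects, normally distributed weight unless stated, and assumed effects; none of the weight or effect assumptions comes from the documents. The subgroup analyses are not primary and no power is claimed for them, so the primary conclusions on HR and RR are untouched.

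**What to change.** In Section 10.5, prespecify for HR and for RR:

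- A linear regression of subject RMSD on continuous weight with linear and squared terms, tested jointly on 2 df at 0.05 and labelled exploratory.
- The fitted mean RMSD with 95% CI across the observed weights, up to the heaviest enrolled and no further.
- A scatter plot of RMSD against weight, and the number of subjects near the 150 kg limit, with the band for near defined before the data are seen.
- The quartile ANOVA as now planned, with the quartile means, alongside the regression.

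This needs a few lines of SAP text and one model per variable on data already collected, with no new visits or subjects. The price is one more exploratory test for each of HR and RR, so the chance of a spurious finding rises somewhat. The change does not make up for few heavy subjects; reporting their number lets a reader see how far the data support accuracy at the limit.

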10.6. Sample Size

In a pilot study of 20 adult healthy volunteers with 20 paired observations each, the standard deviation of their RMSDs vs. the reference method were found to be approximately 0.75 for both HR and RR (2). Based on this standard deviation, 73 adult subjects will provide 80% power to reject each primary hypothesis if the population mean RMSD for HR is 3.0 and the population mean for RR is 2.0. To account for a dropout rate as high as 5%, a total of 77 adult subjects will be enrolled.

SAS Version 9.4 PROC POWER was used for all sample size calculations.

11. Regulatory and Reporting Requirements

11.1. IRB Approval

The investigator will ensure that IRB review and approval are obtained before beginning the study, or allowing any subject to participate. The Investigator will notify the Sponsor of any withdrawal of IRB approval of the study.

Any deviation from the investigational plan shall be reported to the Sponsor, and to the IRB per its requirements. Any revision to this protocol cannot be implemented without approval from the IRB and the Sponsor. The Investigator will submit a final report to the IRB after termination or completion of the study.

11.2. Informed Consent

The Investigator shall ensure that informed consent is obtained from subjects or their guardians.

11.3. Clinical Monitoring

The Sponsor or designee will be responsible for monitoring of compliance with the trial protocol, GCPs, and all applicable federal regulations concerning human subject research. The study monitors will perform on-site monitoring visits, including source document verification, device accountability, and assess compliance with safety reporting in accordance with Sponsor's procedures and all applicable regulatory requirements. The Investigator will agree to give full access of all study data, site procedures, and other relevant information to the study monitor (and auditor if needed) during each site visit.

At the site initiation visit the Sponsor or designee will review the study protocol and all associated study documentation and procedures with the Investigator and study personnel. All site personnel will receive training for device use and use of the data collection tool, as appropriate to their role. In addition, study-specific GCP training will be provided.

During the course of the study, the Sponsor or designee will maintain regular contact with the investigative sites and may conduct on-site monitoring visits and/or source data verification on a regular basis to ensure compliance with this study protocol.

The investigators shall conduct this study in accordance with this protocol. Failure to comply with and/or inability to meet these regulations may jeopardize further participation of the Investigator or investigative site in this and future clinical studies.

Investigators must report major protocol deviations that affect the safety and welfare of subjects or affect integrity of study (or if the investigator deviated from the protocol in order to save a life or prevent further harm to the subject) to the Sponsor within 5 working days of investigational site knowledge of the deviation.

a. Monitoring Method and Times

On-site visits will be made 3 times for each site when:

- the 1st patient completes testing
- the 5th patient completes testing
- the 15th patient completes testing

Remote monitoring will be done for the following items:

- Data on EDC system;
- Feedback from the investigators;
- Signature of the informed consent.

b. On-site monitoring procedures

1. Check if the device is used per the User's Manual.
2. Check if the investigator performs the procedures as per the clinical protocol and if there is any deviation from the protocol.
3. Check if subjects meet the inclusion criteria and excluded per the exclusion criteria.
4. Check if the informed consent is obtained before the testing.
5. Check the data, the date on the CRF. Check the consistency of CRF. Mark the questioned data and require the investigator to validate or correct it.
6. Check device preservation condition and device quantity to make sure to provide supplement in time.
7. Check if there is adverse event and if the adverse event is recorded.
8. Keep the monitoring record.

If there is any discrepancy or inconsistency found in remote monitoring, Sponsor can issue queries and require investigator to submit justification or corrections.

